#### **5.2.5 MRI Assessments**

Volumetric assessments using MRI are collected and analyzed by NIH.

For the purpose of this SAP, MRI data will only be listed.

### **5.3 Exploratory Endpoints**

Biomarkers are collected in blood, urine, and cerebrospinal fluid. Biomarker data is collected and analyzed by NIH.

For the purpose of this SAP, biomarker data will only be listed.

### **5.4 PK Analysis**

A specific PK Analysis Plan was prepared by [REDACTED] PK group describing all analysis of PK endpoints. PK analyses are not in the scope of this SAP.

### **5.5 Subject Disposition**

A tabulation of subject disposition will be provided for all screened subjects and will include:

1. Number of subjects screened,

2. Number (%) of screen failures,
3. Number (%) of subjects enrolled,
4. Number (%) of subjects treated,
5. Number (%) of subjects in each analysis population,
6. Number (%) of subjects who completed the treatment,
7. Number (%) of subjects who did not complete the treatment, and reasons for doing so,
8. Number (%) of subjects who completed the study,
9. Number (%) of subjects who terminated the study early, and reasons for doing so.

**Screened subject** is defined as any subject with informed consent date. **Screen failure** is defined as any subject who answered "NO" to "Did the subject satisfy all the enrollment criteria?" on "Enrollment" eCRF page. **Enrolled subject** is defined as any subject who answered "Yes" to "Did the subject satisfy all the enrollment criteria?" on "Enrollment" eCRF page.

A disposition listing will be created to support the information in the disposition table.

Listings of inclusion/exclusion criteria and enrollment criteria will also be created.

## 5.6 Protocol Deviations

Protocol deviations are defined as activities on a study that diverge from the approved protocol.

Prior to database lock, the Sponsor will produce the final protocol deviation file in collaboration with the data monitoring group; this file will include a description of the protocol deviation, the occurrence date, the categorization as minor / major. This file will be finalized prior to hard database lock.

Protocol deviations data will be listed separately for major and minor deviations.

## 5.7 Demographics and Baseline Characteristics

Demographics information will be summarized using descriptive statistics for the Safety Population and will include:

1. Age (years) at time of informed consent (as continuous variable),
2. Sex (Male / Female),
3. Ethnicity (Hispanic or Latino / Not Hispanic or Latino / Not Reported / Unknown),
4. Race (White / Black or African American / Asian / Native Hawaiian or Other Pacific Islander / American Indian or Alaska Native / Other),
5. Weight (kg; as continuous variable),
6. Height (cm; as continuous variable),
7. Body mass index (BMI; kg/m^2; as continuous variable).

Age at time of informed consent and BMI will be reported as collected on the eCRF. Visit 1 weight, height and BMI are reported for this summary (as height and BMI are only measured at Visit 1).

Demographics and baseline characteristics data (including information on childbearing potential, where applicable) will be listed.

Baseline disease characteristics will be summarized using descriptive statistics for the Efficacy Population and will include baseline information regarding the following:

1. CLN3 mutations: CLN3 variants identified? (Yes / No / Unknown)
  - a. Variant 1
  - b. Variant 2
2. UBDRS Neuronal Ceroid Lipofuscinosis (NCL) history domain:
  - a. 58a. Loss of vision,
  - b. 58b. Motor difficulties,
  - c. 58c. Cognitive difficulties,
  - d. 58d. Behavioral difficulties,
  - e. 58e. Seizures,
  - f. 58f. Feeding difficulties,
  - g. 58g. Sleep disturbances,
  - h. 58h. Others.

For both Variant 1 and Variant 2 CLN3 mutations the following data will be summarized:

1. Segregation (Maternal / Paternal / Unknown),
2. DNA change notation,
3. Protein change notation,
4. Zygosity (Homozygous / Heterozygous / Unknown / Other),
5. Classification (Pathogenic / Likely Pathogenic / Likely Benign / Benign / Uncertain Significance),
6. Secondary confirmation performed (Yes / No).

For each of UBDRS NCL history domain questions, the following data will be summarized:

1. Experienced symptoms? (Yes / No / Not Done),
2. Onset age in years,
3. Ranking (order of onset of symptoms, 1-8).

The onset age in years is derived as:

*Onset age years (collected in eCRF) + [Onset age months (collected in eCRF)] / 12,*  
e.g., if onset age years is entered as 1 and onset age months is entered as 6, then onset age in years will be calculated as  $1 + 6/12 = 1.5$  (years).

Baseline disease characteristics data will be listed.

## 5.8 Prior and Concomitant Medications

Prior and concomitant medications will be coded using the latest version of World Health Organization Drug Dictionary (WHODD) available before the database lock.

Prior medications are those which have been identified to have been discontinued prior study drug start date (i.e., taken exclusively before treatment start). Concomitant medications are those which have been identified to have been taken at any point on or after the study drug start date. If it is not possible to determine whether a medication is prior or concomitant, it will be assumed to be concomitant.

Partial start and end dates of medications will be imputed according to section [8.1](#) for the determination of prior and concomitant designations.

The incidence of concomitant medication use will be summarized for the Safety Population by WHODD anatomic therapeutic chemical (ATC) Level 2 classification (i.e., therapeutic main group) and preferred name. A subject will be counted only once at each level of reporting. Prior medication use will only be listed.

Prior and concomitant medication data will be listed.

### **5.9 Concomitant Procedures**

Concomitant procedures will be coded based on the Medical Dictionary for Regulatory Activities (MedDRA) latest version available before the database lock.

Concomitant procedure data will be listed.

### **5.10 Exposure to and Compliance with Study Drug (Miglustat)**

Miglustat administration data will be summarized for the Safety Population by visit and will include the following variables:

1. Was the study drug administered? (Yes / No),
2. Study drug dose / day (mg) (continuous variable),
3. Study drug dose / day (mg) (categorical variable – 100 / 200 / 300 / 400 / 500 / 600).

Miglustat administration data (including supply and accountability) will be listed for the Safety Population.

Note that in initial protocol versions, Trehalose was planned to be administered alongside miglustat. However, the protocol and eCRF were amended before any subject received Trehalose. Therefore, no data will be presented for Trehalose.

### **5.11 Medical History**

Medical history terms will be coded based on the Medical Dictionary for Regulatory Activities (MedDRA) latest version available before the database lock.

A table will be generated to summarize medical history for the Safety Population by SOC and PT. A subject will be counted only once at each level of reporting.

Medical history data will be listed.

### **5.12 General Aspects for Statistical Analyses**

- Categorical variables will be summarized using the number of observations (n), frequency and percentage of subjects. All percentages will be presented as one-decimal point, unless otherwise specified. Percentages equal to 100 will be presented as 100% and percentages will not be presented for zero frequencies.
- Continuous variables will be summarized using the number of subjects with evaluable data (n), mean, standard deviation (SD), geometric mean (where appropriate), median, minimum and maximum. In general, the same number of decimal places as in the raw data will be presented when reporting minimum and maximum, 1 more decimal place than in the raw data will be presented when reporting the mean and median, and 2 more decimal places than in the raw data will be presented when reporting the SD.
- Unless stated otherwise, the percentages will be based on the number of non-missing observations. The column header will still contain the number of subjects in the treatment group. Where appropriate, there will be a row for the number of non-missing observations in the table (at each time point, if required) for each variable being summarized.
- All relevant subject data will be included in listings and sorted by treatment group (treated subjects first, followed by screen failures), subject ID, visit/timepoint, and assessment type, as applicable. All listings (except for study drug exposure) will be based on All Screened Subjects.
- Unscheduled or repeat assessments will not be included in summary tables unless specified. All assessments will be included in the subject listings.
- All tables, listings and figures will include footers that identify the name of the program that created the output, together with the date and time on which it was created. Headers will include the total number of pages that the presentation contains and, for each page, the number of the page within the presentation.

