#### **Symptoms**

No acute symptoms of overdose have been identified. Zavesca has been administered at doses up to 3000 mg/d for up to 6 months in HIV-positive subjects during clinical trials. Adverse events observed included granulocytopenia, dizziness, and paresthesia. Leukopenia and neutropenia have also been observed in a similar group of subjects receiving 800 mg/d or higher dose.

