#### 7.1.1 Adverse Events

##### 7.1.1.1 Definitions

Adverse events and laboratory parameters will be graded using the National Cancer Institute (NCI) Common Terminology Criteria for Adverse Events (CTCAE) v5, sample of which is provided in Appendix 7 (US Department of Health and Human Services, 2017).

Per ICH, an AE is defined as any untoward medical occurrence in a subject or clinical investigation subject administered a pharmaceutical product and which does not necessarily have a causal relationship with this treatment. An AE can therefore be any unfavorable or unintended sign (including an abnormal laboratory finding), symptom, or disease temporally associated with the use of a medicinal (investigational) product, whether or not related to the medicinal (investigational) product. The AE may be any of the following:

- A new illness
- An exacerbation of a sign or symptom or the underlying condition or of a concomitant illness under treatment
- Unrelated to participation in the clinical study or an effect of the study medication or comparator drug
- A combination of one or more of the above factors

No causal relationship with the study medication is implied by the use of the term adverse event.

Planned or elective surgical or invasive procedures for pre-existing conditions that have not worsened are not AEs. However, any complication that occurs during a planned or elective surgery is an AE. Conditions leading to unplanned surgical procedures may be AEs.

When an AE occurs after written consent has been obtained but before the first dose of study drug, the AE will be considered a non-treatment emergent AE. An AE that occurs from the time the subject receives his/her first dose of study drug until his/her last study visit will be considered a treatment-emergent AE regardless of the assessed relationship to the administration of the study drug.

For the recording of pregnancy and relevant laboratory data see [Section 7.1.1.2](#).

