## **2.2 Study Sample Size Determination**

A total of six subjects will be enrolled in the study. Due to the ultra-rare nature of CLN3 disease, sample size is based on subject availability and not a statistical determination.

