**Table 1. Study Objectives and Endpoints**

Objectives	Endpoints
Primary	

 
To assess the safety and tolerability of the Batten-1 treatment regimen over the study period
 
	
 
Incidence of treatment-emergent adverse events (TEAEs) and serious adverse events (SAEs);
 
Changes from baseline in clinical laboratory tests (hematology, chemistry, and urinalysis), 12-lead electrocardiogram (ECG) findings, slit lamp evaluation, vital signs (heart rate and blood pressure) as well as physical and neurological examinations
 

Secondary	

 
To assess the pharmacokinetics (PK) of miglustat in subjects with CLN3 disease
 
	
 
Week 1 first dosing: Maximum plasma concentration (Cmax), Time to Cmax (Tmax), area under the concentration-time curve calculated to the last observable concentration at time t (AUC 0-t), area under the concentration-time curve extrapolated to infinity (AUC 0-∞), elimination half-life (T1/2)
 
Week 9 - Repeated dose (steady state): Cmin, Cmax, Tmax, AUC 0-8hr
 

 
To assess the effect of the Batten-1 treatment regimen on the longitudinal progression of clinical symptoms of CLN3 disease
 
	
 
Unified Batten Disease Rating Scale (UBDRS)
 
Seizure frequency (diaries)
 
Vineland Adaptive Behavior Scales, Version 3 (Communication, Daily Living Skills, Socialization, and Motor Skills domains)
 
Ophthalmic assessments including visual acuity, visual fields (if feasible), and optical coherence tomography (OCT)
 
Magnetic resonance imaging (MRI)
 

Exploratory	

 
To assess potential biomarkers of CLN3
 
	
 
Measure biomarkers in cerebrospinal fluid (CSF), blood and urine and CSF concentration of miglustat
 

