### **5.1.2 Clinical Laboratory Tests**

Hematology, biochemistry, and urine results will be reported using standard units as provided by central laboratory; no further standardization is applied by [REDACTED].

Lab values below lower limit of quantification (LLOQ) will be imputed as  $\frac{1}{2}$  LLOQ. Lab values above upper limit of quantification will (ULOQ) will be imputed as  $1.1 * \text{ULOQ}$ .

The following clinical laboratory evaluations will be reported:

1. **Hematology:** hemoglobin, hematocrit, erythrocytes, leukocytes, differential white blood cell count, thrombocytes.
2. **Biochemistry:** creatinine, total bilirubin (direct and indirect if values were above normal ranges), hemoglobin A1c (HbA1c), alkaline phosphatase, aspartate aminotransferase, alanine aminotransferase, gamma glutamyl transpeptidase, creatinine kinase, sodium, potassium, cholesterol (total, HDL, LDL), triglycerides, creatinine clearance.
3. **Urine:** glucose, nitrate, pH, hemoglobin, leukocytes, specific gravity, protein, ketones.
4. **Other tests:** HIV, hepatitis B, hepatitis C.
5. **Pregnancy test:** urine/serum.

Observed values and changes from baseline for hematology and biochemistry will be summarized at each scheduled post-baseline visit. Baseline will be defined as last value collected before first study drug administration (both dates and times will be compared); both data collected at scheduled and unscheduled visits will be included in baseline derivation.

Additionally, shift tables from baseline to each scheduled post-baseline visit will be added for select laboratory parameters: thrombocytes, and creatinine kinase. Lab values will be classified as low, normal, and high for the purpose of shift table creation.

Urinalysis overall interpretation (Abnormal – Clinically Significant / Abnormal – Not Clinically Significant / Normal) will be presented by visit in a frequency table. Urinalysis results by parameter will only be listed.

Laboratory data will be listed.

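### The SAP does not carry out the protocol's CTCAE grading of laboratory values, and separately keeps post-baseline unscheduled results out of every laboratory summary table

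*SAP*

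**What the plan says.** Laboratory change is part of the primary safety endpoint. SAP Table 1 lists "Changes from baseline in clinical laboratory tests (hematology, chemistry, and urinalysis") beside the incidence of adverse events.

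**Grading.** Protocol 7.1.1.1 begins: "Adverse events and laboratory parameters will be graded using the National Cancer Institute" criteria, version 5. SAP 5.1.1 assigns CTCAE v5.0 to the investigators' grading of adverse events. SAP 5.1.2, on laboratory tests, gives no grading rule. It uses low, normal and high only to build shift tables, and limits these: "shift tables from baseline to each scheduled post-baseline visit will be added for select laboratory parameters: thrombocytes, and creatinine kinase". SAP 1.1 lists two changes from the protocol (an added MedDRA level in the adverse event tables, and dictionary versions). Laboratory grading is not one of them.

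**Which results are tabulated.** Under SAP 5.1.2, hematology and biochemistry are summarized as observed value and change at each scheduled post-baseline visit. Urinalysis gets an overall interpretation by visit, with individual parameters listed only. For laboratory data, the one stated use of unscheduled results in a summary is before dosing: "both data collected at scheduled and unscheduled visits will be included in baseline derivation". After baseline the general rule in SAP 5.12 applies: "Unscheduled or repeat assessments will not be included in summary tables unless specified". The same section puts all assessments in the listings and has continuous summaries report minimum and maximum as well as mean, SD and median.

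**The concern.** There are two separate gaps.

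The first is a mismatch between documents. The protocol commits to grading laboratory parameters, the SAP has no step that does it, and the SAP's own list of changes is silent. A reader of the final report could not tell whether grading was overlooked or deliberately dropped.

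The second concerns coverage. Tables confined to scheduled visits describe the laboratory profile on a few fixed dates. A draw made between those dates because something looked wrong is by nature unscheduled, and the SAP leaves its result out of the laboratory summaries. If the value has recovered by the next scheduled visit, those summaries contain no trace of it. In a safety study of six subjects, a single such event is a sizeable part of the information that the laboratory component of the primary endpoint can provide.

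**Working it through.** No power, error rate or sample-size figure is involved. The analysis is descriptive, and SAP 2.2 says the "sample size is based on subject availability and not a statistical determination". The check is a cross-reading with a few counts.

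**1. Is laboratory grading planned anywhere in the SAP?**

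| Source | Adverse events | Laboratory values |
|---|---|---|
| Protocol 7.1.1.1 | CTCAE v5 | CTCAE v5 |
| Protocol 8.7 | Tabulated by severity | Descriptive, by visit or timepoint |
| SAP 5.1.1 | CTCAE v5.0 by investigators | – |
| SAP 5.1.2 | – | Low/normal/high, two parameters only |
| SAP 1.1 | No change to grading listed | No change to grading listed |

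It is not. The conflict is with protocol 7.1.1.1. Protocol 8.7 promises no table of laboratory grades.

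**2. How much categorical summary is there?** Counting the SAP 5.1.2 list:
- Hematology: 8, with the differential counted as neutrophils, lymphocytes and monocytes.
- Biochemistry: 15, with cholesterol counted as total, HDL and LDL, and conditional direct/indirect bilirubin not counted.
- Total: 8 + 15 = 23. With the differential as one item, 23 − 2 = 21. With cholesterol also as one, 21 − 2 = 19.

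Shift tables cover 2 of 19 to 23 parameters, and neither is leukocytes or neutrophils. Grade tables cover none.

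**3. How long are the gaps between scheduled post-dose draws?** Protocol 4.1 and 7.1 give Week 6 and then every 6 months. Table 1-2 gives Weeks 26, 52 and 78 and the final visit.
- Week 6 to 26: 26 − 6 = 20 weeks
- Week 26 to 52: 52 − 26 = 26 weeks
- Week 52 to 78: 78 − 52 = 26 weeks
- Week 78 to the final visit: up to 116 − 78 = 38 weeks, if a subject reaches the 116-week treatment limit in the synopsis. Table 1-5 shows no safety laboratory tests at Weeks 82 or 94.

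These are nominal. The one-month windows around Weeks 26, 52 and 78 can shorten or lengthen them.

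**4. Where does an unscheduled abnormal value go?** Suppose it is drawn in one of these gaps and is normal again at the next scheduled visit.
- Hematology or biochemistry by-visit table: not included (SAP 5.1.2, 5.12).
- Shift table: not included, because these are also built by scheduled visit.
- Worst-value or any-time table: none is planned.
- Listings: included (SAP 5.1.2, 5.12).
- Adverse event tables: included with a grade if the investigator judges the change clinically relevant. If it is a sign of an event already recorded, that event is counted (protocol 7.1.1.5; SAP 5.1.1).

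**5. Which rule causes the omission?** Only the restriction to scheduled visits together with the exclusion of unscheduled results. Grades or further shift tables built by scheduled visit would not bring the value in, so the two gaps need separate repairs.

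**6. Size for one subject:** 1/6 = 16.7% of the planned sample.

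**The case against.** The best defence is that little is lost. A clinically relevant value is an adverse event and enters the tables by maximum CTCAE grade and of Grade 3 or above. Those tables serve the first-named part of the same primary endpoint. Absence from every table therefore needs an unscheduled draw, recovery before the next visit, no recorded event of which the value is a sign, and an investigator's judgement that it was not relevant. Even then the listing has it, and the listings of six subjects can be read in full. The grading sentence also sits in the adverse event definitions, while protocol 8.7 asks only for descriptive statistics by visit, which the SAP delivers. On that view a worst-grade table is partly a matter of preference.

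Most of this stands, and it limits the weight of the point. It does not remove it. The adverse event route depends on judgement, whereas the grading sentence names laboratory parameters in their own right. A listing is also not a summary.

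Stronger readings that a reader might infer are not supported:
- **That the tables would hide a low count in general.** SAP 5.12 prints the minimum and maximum, so an extreme at a scheduled visit is visible, although without a grade or a link to that subject's baseline category.
- **That cytopenia is to be expected here.** Protocol 6.9.1 does say "Adverse events observed included granulocytopenia, dizziness, and paresthesia", and goes on to leukopenia and neutropenia. That is overdose text about HIV-positive subjects: the first group received up to 3000 mg/d, and the leukopenia and neutropenia were seen at 800 mg/d or more. This trial's maximum is 600 mg/d, and HIV is an exclusion criterion. The miglustat risk section (protocol 2.3.1.1) names no cytopenia.
- **That the laboratory result is biased toward no change by some amount.** The documents give no frequency of unscheduled draws and plan no test or effect estimate for laboratory change. Using unscheduled values to fix the last pre-dose baseline is also not in conflict with by-visit tables afterwards.

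**Conclusion.** The point holds as two distinct gaps of moderate weight. First, the SAP neither implements the laboratory grading stated in protocol 7.1.1.1 nor records that it is dropped. Second, an abnormal result from an unscheduled post-baseline draw that recovers by the next scheduled visit appears in none of the planned laboratory summary tables. The gaps in which this can happen are nominally 20 to 26 weeks up to Week 78, and up to 38 weeks afterwards for a subject treated to Week 116.

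The omission follows from the SAP's stated rules. How often it would occur cannot be derived from the documents. The result would still be in the listings and, by the routes described above, may be in the adverse event tables. The summary of part of the primary endpoint is therefore incomplete, but the data are kept. This is worth correcting before database lock because the remedy is cheap.

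**What to change.** 1. In SAP 5.1.2, state how CTCAE v5 grades will be derived for gradable laboratory parameters, in line with protocol 7.1.1.1.
2. Add one table of baseline grade by worst post-baseline grade per subject, using scheduled, unscheduled and repeat results. Include leukocytes and neutrophils. Where a parameter can be abnormal in either direction, show low and high separately.
3. In SAP 5.12, name this table as an exception to the rule on unscheduled and repeat assessments. Leave the by-visit and shift tables unchanged.
4. If laboratory grading has been dropped on purpose, record that with the reason in SAP 1.1, and build the worst-value table on low/normal/high instead.

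The cost is SAP wording, one derived variable and one table, all from data already collected. The downside is that a worst-value table will show some isolated or transient values. The listings can supply the context for each in a study of this size.
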